6.4.1. Safety Criteria for Adjustment or Stopping Doses

1. If more than 5 volunteers in any group have an unexplained CD4 cell count decline (confirmed by assays at least 4 weeks apart) of greater than 30 percent and corroborated by a similar CD4% decline (>30%), immunizations in that study group will be stopped. No further immunizations will be allowed until after all data are reviewed by the IHV DSMB and the DSMB authorizes immunizations to continue in this group. Follow-up visits for safety will continue during this time. Note that an unexplained drop in CD4 cell count is defined as a decline that cannot be explained by an intercurrent illness or other event known to cause decreased CD4 cell counts.
2. The entire study will be stopped if five or more vaccine related severe (grade 3 or 4) adverse events occur in any group.
3. The volunteer will have immunizations stopped upon the occurrence of an unexpected Grade IV event felt by the investigator to be related to the study vaccine. No further immunizations will be allowed until after all data are reviewed by the IHV DSMB and the DSMB authorizes immunizations to continue in this group. Follow-up visits for safety will continue during this time.
4. The entire study immunizations will be stopped upon the occurrence of one unexpected serious adverse event felt to be related to the study vaccine.

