6.5. Criteria for Study Termination

Criteria for Termination of Study immunizations in all volunteers.

1. The entire study will be stopped upon the occurrence of an unexpected Grade 3 or 4 event thought to be related to the study vaccine in 5 volunteers as noted in [Section 6.4.1](#). If after review by the DSMB, these events are determined by the DSMB to be study vaccine related, the volunteers would be continued to be followed on the study for safety, but no further immunizations would occur in any of the groups.
2. Individual volunteers may have immunizations halted as listed in [Section 6.4.1](#).

Table 3: Study Design

Phase 1 FLSC Study Immunization Schedule/Volunteer Allocation							
Group	Route of Administration	N Vaccine/Control	Vaccine Dose	Vaccination Schedule in Months (Days)			
				0	1(28)	2(56)	6(168)
1	IM	15	0.25 ml (75 ug)	FLSC/ ALPO4	FLSC/ ALPO4	FLSC/ ALPO4	FLSC/ ALPO4
		5	0.25 ml	Saline	Saline	Saline	Saline
2	IM	15	0.5 ml (150 ug)	FLSC/ ALPO4	FLSC/ ALPO4	FLSC/ ALPO4	FLSC/ ALPO4
		5	0.5 ml	Saline	Saline	Saline	Saline
3	IM	15	1.0 ml (300 ug)	FLSC/ ALPO4	FLSC/ ALPO4	FLSC/ ALPO4	FLSC/ ALPO4
		5	1.0 ml	Saline	Saline	Saline	Saline
TOTALS		60					

Table 4: Schedule of Assessments

STUDY VISIT	0	01	02	03	04	05	06	07	08	09	10	11	12	13	14 ³				
STUDY DAY	-30 TO -3	0	1-2	14	28	29-30	42	56	57-58	70	84	112	168	169-170	182	196	252	294	336
STUDY WEEK	-4 TO -0	0	2	4	6	8	10	12	16	24	26	28	36	42	48				
Informed Consent	X																		
Immunization		X		X		X		X				X							
Complete Medical History and Physical Examination	X																		X
Interval Medical History and Directed Physical Examination(as indicated)		X		X	X		X	X		X	X	X	X		X	X	X	X	
Phone Interview			X			X			X					X					
Dispense diary		X			X			X					X						
Monitor Adverse Events		X	X	X	X	X	X	X	X	X	X	X	X	X	X	X	X	X	X
Blood for Screening Labs: CBC with diff Serum Chemistry, LFT's PT/PTT Hepatitis B Surface Antigen Hepatitis C Antibody ¹ CD4 cell count HIV-1 RNA PCR HIV-1 ELISA/Western blot	X																		X
Pregnancy Test (serum)	X																		
Pregnancy Test (urine)		X			X			X					X						X
Urinalysis	X																		X

STUDY VISIT	0	01		02	03		04	05		06	07	08	09		10	11	12	13	14 ³
Blood for Safety Labs: CBC with diff Serum Chemistry, LFT's CD4 cell count HIV-1 RNA PCR ²		X		X	X		X	X		X	X	X	X		X	X	X	X	
Blood for Serologic Assays/Serum storage	X	X ⁴		X ⁴	X ⁴		X ⁴	X ⁴		X ⁴	X	X ⁴	X ⁴		X ⁴	X	X ⁴	X	X ⁴

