7.3.4. Reasons for Discontinuation of all Immunizations in the Study

All immunizations across the entire study will be stopped upon the occurrence of 5 or more unexpected Grade 3 or 4 events felt to be related to the study vaccine in any group or a serious adverse event felt to be related to study vaccine in one volunteer as noted in [Section 6.4.1](#) and [Section 6.5](#). Follow-up visits for safety will continue to occur as per study protocol. No further enrollments will occur.

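### After a study-wide Grade 3/4 halt, Section 7.3.4 closes enrollment without condition while Section 6.5 makes the end of immunizations depend on a DSMB finding

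*Combined protocol and SAP*

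**What the plan says.** Three sections of the protocol deal with a study-wide halt for Grade 3 or 4 events.

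- **Section 6.4.1, item 2:** "The entire study will be stopped if five or more vaccine related severe (grade 3 or 4) adverse events occur in any group". It has no review step, no restart route and no statement on enrollment.
- **Section 6.5, item 1:** the study stops on an "unexpected Grade 3 or 4 event thought to be related to the study vaccine in 5 volunteers". What follows is conditional: "If after review by the DSMB, these events are determined by the DSMB to be study vaccine related", safety follow-up goes on, "but no further immunizations would occur in any of the groups". Enrollment is not mentioned, and neither is the case where the DSMB finds the events unrelated.
- **Section 7.3.4:** "All immunizations across the entire study will be stopped upon the occurrence of 5 or more unexpected Grade 3 or 4 events" that are felt to be related, in any group. It cites 6.4.1 and 6.5, keeps the safety visits going, and ends with "No further enrollments will occur".

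Section 7.3.4 also has a second trigger, "a serious adverse event felt to be related to study vaccine in one volunteer". Its counterpart is item 4 of 6.4.1: "The entire study immunizations will be stopped upon the occurrence of one unexpected serious adverse event felt to be related to the study vaccine". Section 6.5 has no such trigger.

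**The concern.** A halt rule has to tell the site and the DSMB what happens next. Here one section makes the lasting consequence depend on the DSMB's judgment of relatedness, another closes enrollment at once, and a third says only that the study stops. Nothing says which section controls: Section 13.7 cites 6.4.1, 6.5 and 7.3 together for discontinuation and ranks none of them.

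Enrollment matters in this design because it is sequential. Section 6.3 fills each group before the next opens, and Section 6.4 requires DSMB review and approval at each step up. A halt arising in Group 1 or 2 can therefore come before a later dose group has been enrolled. Section 4.2 says the trial is meant to choose a dose for future trials, so whether enrollment can reopen bears directly on its purpose. The ambiguity would come to light during a live safety halt, when it is hardest to settle.

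**Working it through.** No figure in the plan needs reproducing. The check is a comparison of the texts, followed by one count.

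**Step 1. The sections side by side, for the Grade 3/4 halt**

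| Question | 6.4.1 item 2 | 6.5 item 1 | 7.3.4 |
|---|---|---|---|
| What stops at the trigger | Entire study | Entire study (the section's lead line speaks of immunizations in all volunteers) | All immunizations |
| DSMB determination of relatedness | None | Required before immunizations end in all groups | None in its own text; cites 6.4.1 and 6.5 |
| If the DSMB finds the events unrelated | Silent | Silent; the stated condition is not met | Silent |
| Restart route | None | None written | None |
| Enrollment | Silent | Silent | Closed, no condition |
| Safety follow-up | Silent | Continues | Continues |

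**Step 2. Follow each DSMB finding through**

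- *Events related.* Sections 6.5 and 7.3.4 agree that immunizations end. Section 7.3.4 adds that enrollment ends, and 6.5 says nothing against it. There is no practical conflict.
- *Events unrelated.* The condition in 6.5 for ending immunizations fails, which implies that they could resume. Under 7.3.4 enrollment has already closed, with no way back. The sections do not give one outcome.

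**Step 3. Does the protocol write a restart route elsewhere?**

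Yes. For the CD4 decline halt (6.4.1 item 1 and 7.3.3) and for an individual Grade IV event (6.4.1 item 3), immunizations are barred until the DSMB has reviewed the data and authorized continuation. No equivalent sentence appears in 6.4.1 item 2, 6.5 item 1 or 7.3.4. Its absence may be intended or an oversight; the text does not show which.

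**Step 4. What closing enrollment could remove**

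Inputs from Table 3: three groups, each with 15 vaccine and 5 saline recipients, 60 in all.

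- Halt before Group 2 opens: 2 × 20 = 40 of 60 not enrolled (30 vaccine, 10 saline). Only the 75 µg group remains, so doses cannot be compared.
- Halt after Group 2 is full and before Group 3 opens: 20 of 60 not enrolled (15 vaccine, 5 saline). The 300 µg group is missing.
- Halt while a group is filling: a number in between.

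These counts describe the consequence once a halt has occurred. The documents give no expected rate of related Grade 3 or 4 events, so the chance of a halt cannot be stated.

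**Step 5. The serious-adverse-event trigger**

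Section 6.5 does not cover it, and item 4 of 6.4.1 gives no DSMB determination for it. For this trigger the DSMB step is absent, not contradicted.

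**The case against.** The best defense is that 7.3.4 cites 6.4.1 and 6.5, and 6.5 cites 6.4.1, so the three form a chain: stop, DSMB review, no more immunizations if the events are related. That works for immunizations. It does not reach the enrollment sentence, which stands alone and carries no condition, and 6.5 has no enrollment rule to import.

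A second defense is that the texts are logically compatible: enrollment closes on any halt, and the DSMB finding governs only the remaining injections of those already enrolled. That is possible, but no section says it.

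Third, Section 11.6 lets the DSMB recommend or mandate changes, and Section 17 provides for formal amendment, so 7.3.4 need not be the last word. This stands. It is why the effect on later groups is something that could happen and not a certainty. Also, every section stops dosing once its own trigger is met, so the disagreement is about what follows the stop.

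Fourth, the triggers are not identical. Section 6.5 counts volunteers, 6.4.1 and 7.3.4 count events in any group, and item 2 of 6.4.1 omits the word unexpected. That is a separate inconsistency. It does not remove this one, because 7.3.4 presents its halt as the one in 6.4.1 and 6.5.

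Three stronger readings are tempting and are not supported:

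- *That 6.5 allows resumption.* It only implies it, through its condition; no sentence authorizes a restart.
- *That a saline recipient among the five would lift the halt under 6.5.* Relatedness is judged blind, so saline recipients can count toward the trigger, but no section says the halt lapses when fewer than five of those counted received vaccine. The chance of a saline recipient being among the five therefore does not measure this conflict.
- *That the DSMB holds the treatment codes.* Section 8.4.2 leaves one envelope with the investigator and the other with the research pharmacy or medical monitor; Section 11.6 gives the DSMB access.

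**Conclusion.** The inconsistency is real and narrow. It bites in one case: a study-wide Grade 3/4 halt that the DSMB then judges unrelated to vaccine. There the condition in 6.5 for ending immunizations is not met, 7.3.4 has closed enrollment with no restart route, and 6.4.1 item 2 is silent on both. If 7.3.4 were followed as written, 20 to 40 of the 60 planned volunteers would not be enrolled when the halt falls between groups.

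This rests on reading the enrollment sentence literally and on the three sections describing essentially one halt, as their cross-references indicate. It does not rest on any assumed event rate. The issue is one of drafting, but it should be corrected, because in a sequential design it can decide which doses are studied. A reader might extend the contradiction to the single serious-adverse-event trigger; the documents show only a gap there. Nor is safety follow-up in dispute between 6.5 and 7.3.4, since both continue it; only 6.4.1 item 2 leaves it unsaid.

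**What to change.** Reconcile 6.4.1 item 2, 6.5 item 1 and 7.3.4 into one rule, stated once and cited from the other places. The rule should say:

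- whether the halt is provisional pending DSMB review or final;
- how that applies to immunizations and, separately, to enrollment, including later dose groups;
- what follows if the DSMB finds the events unrelated;
- that safety follow-up continues, so that 6.4.1 item 2 matches 6.5 and 7.3.4.

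The same edit should state the DSMB's role for the single serious-adverse-event trigger, where the text is silent. Which consequence applies is for the sponsor and the DSMB to decide. The cost is amendment wording and the approval that goes with it, with no change to sample size, visits or data collection.

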8. TREATMENT OF VOLUNTEERS

8.1. Description of Study Drug

The FLSC final product consists of 0.3 mg/ml of purified FLSC Drug Substance formulated with Aluminum Phosphate (AlPO_4) at 2.4 mg/mL in binding buffer (mannitol 40 mg/mL; sodium acetate 5 mM, pH 6.2. Aluminum ion concentration is 1.2 mg/mL and 1.3 mL product is vialled in 2cc glass vials.

Table 6: Investigational Product

	Investigational Product	
Product Name:	IHV01	0.9% Sodium Chloride Inj., USP
Dosage Form:	1 ml single dose vial	Liquid
Unit Dose	300 ug/vial	10 ml/ single dose vial
Route of Administration	Intramuscular	Intramuscular
Physical Description	FLSC 0.3 mg/ml, Aluminum Phosphate 2.4 mg/ml, Mannitol 40 mg/ml, Sodium Acetate 5 mM	NaCl 9 mg/ml Preservative Free
Manufacturer	Profectus Biosciences	Hospira, Inc.*

*The company the saline is purchased from may change depending on what vendor the institution is using at the time that the trial begins.

8.2. Concomitant Medications

Concurrent medications (with the exception of those noted in the Exclusion Criteria) will be permitted as medically necessary during the study. Changes in medication treatment during this protocol will be permitted if clinically indicated at the discretion of the patient's primary care physician. All changes in medications will be recorded. Medically indicated vaccines (FDA approved; e.g. influenza, pneumococcal, etc.) should be administered either 30 days prior to or following study vaccine administration to minimize potential confusion of adverse experiences due to the study vaccine vs the other vaccine.

8.3. Treatment Compliance

Adherence with the protocol will be assessed by the study personnel at each clinic visit. Careful review of the volunteers' interim medical history will be performed. If appropriate, corroboration of any outside medical clinic or hospital visits will be obtained with the volunteer's consent.

8.4. Randomization and Blinding

Volunteers will be randomized using block randomization in a 3:1 ratio of FLSC:placebo. They will be block randomized in groups of 4 with each study group. This will be done by the research pharmacist utilizing random # generator called Stat Trek. There will be 5 groups of 4 volunteers in each randomized block (each block will have 3 FLSC recipients and 1 placebo recipient).

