2. SYNOPSIS

Name of Sponsor/Company: Sponsor: Institute of Human Virology Manufacturer: Profectus Biosciences	
Name of Investigational Product: IHV01	
Name of Active Ingredient: Full Length Single Chain (FLSC), Aluminum Phosphate	
Title of Study: A Phase I Safety and Immunogenicity Trial of IHV01, in HIV-1 Uninfected Volunteers	
Study center(s): Institute of Human Virology	
Principal Investigator: [name], M.D. Investigators: [name]. [name].	
Studied period (years): 1 year Estimated date first patient enrolled: November 2015 Estimated date last patient completed: May 2018	Phase of development: I
Objectives: Primary: To evaluate the safety and tolerability of intramuscular administration of the IHV01 at three different doses. Secondary: To evaluate the immunogenicity of three different doses of the IHV01, a full length single chain (FLSC) gp120-CD4 complex vaccine. This will be assessed by the following parameters: 1) anti-FLSC antibodies, and 2) anti gp-120 (BaL), and 3) competitive titers to CD4i epitopes.	
Methodology: Single center, randomized, dose escalation, placebo-controlled, double-blind trial	
Number of patients (planned): 60	
Diagnosis and main criteria for inclusion: Inclusion/Exclusion Criteria as in Section 7.1 and Section 7.2 .	
Investigational product, dosage and mode of administration: IHV01 in sequential dose escalation of 75 ug, 150 ug and 300 ug administered intramuscularly.	
Duration of treatment:	

Volunteers will be immunized with candidate vaccine or placebo on Days 0, 28(week 4), 56(week 8), and 168(week 24). Volunteers will continue to undergo active protocol follow up visits on Days 182(week 26), 196(week 28), 252(week 36), 294 (week 42) and 336 (week 48). The total trial time expected per volunteer is 48 weeks. The protocol recruitment period is expected to be approximately 36 weeks. The total trial duration is estimated to be approximately 72-96 weeks.

Reference therapy, dosage and mode of administration:

Placebo consisting of preservative free normal saline in volumes equal to the investigational product administered intramuscularly.

Criteria for evaluation:

Safety:

1. Monitoring and assessment of hematological, chemical, and immunologic parameters (See [Section 11.1.5](#), [Section 12.1](#), and [Table 4](#)).
2. Monitoring participants for local and systemic adverse reactions after each injection and for 12 months after the first injection ([Section 11.2](#)).
 - a. Local reactogenicity signs and symptoms

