4.2. Trial Design Overview

This study is designed to evaluate the safety of the IHV01 vaccine and will be a randomized, placebo-controlled, modified double-blinded dose escalation study in 60 healthy adult volunteers. Although there is a great deal of experience with protein vaccines, the optimal dose of IHV01 given intramuscularly is not known. Therefore, this trial is designed as a dose escalation trial in order to determine the optimal dose to move forward with in future clinical trials. This dose will be chosen after reviewing the safety and immunogenicity data from this trial. Alum has been chosen as an adjuvant due to the extensive amount of safety data available. The study will have 3 arms including placebo, 75 µg dose, 150 µg dose, and 300 µg dose and will last for 336 days (48 weeks). Volunteers will be immunized on Day 0, Day 28(4 weeks), Day 56(8 weeks), and Day 168(24 weeks). Each dose group will have 15 vaccine and 5 placebo recipients. The dosage schedule in this trial was based on the animal data and data with other envelope protein vaccines, and is patterned after the schedule utilized in the RV144 trial in Thailand. From this trial, an optimal dose of the candidate vaccine will be chosen for use in future trials. It is anticipated that the trial will be enrolled and completed 18 months after it is open to enrollment.

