8.4.1. Blinding

Both the investigator and the volunteer will be blinded to the study drug/placebo but not to the group assignment as it is a dose escalation trial. The syringes containing the study drug/placebo will be covered by the study pharmacist to insure blinding of the study.

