8.4.2. Blinding and Code Breaking Procedures

Dose labels will not allow for identification of treatment. The investigator and volunteer will not know which treatment is administered. The pharmacist responsible for product preparation will prepare the appropriate product

for the volunteer as indicated by the block randomization and cover the syringe to prevent identification. The nurse/physician responsible for injection and the volunteer will not know which product is injected as the syringes will be blinded (a film will be affixed on each syringe by the staff responsible for product preparation).

Consequently, two sealed envelopes for each volunteer containing emergency decoding information for each volunteer will be issued by the research pharmacist. The emergency decoding information indicates the treatment corresponding to each randomization number. One envelope will be retained by the investigator and the other one by the research pharmacy/medical monitor.

The code can be broken by opening the individual envelope for the volunteer. The vaccine/diluent injected will be indicated in the envelope. The code may be broken only in case of a Serious Adverse Event and if identification of the treatment can influence the treatment of the adverse event.

In case of code breaking, the name of the person who requests it, the date and reason must be written on the list. The event must be immediately reported on the CRF. The sponsor will immediately be informed by phone or by fax.

At the end of the trial the emergency decoding information will be returned to the sponsor and checked. In the absence of any problem, codes will be broken at the time of the analysis, when the data base is validated and locked.

[figure not shown]

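### Section 8.4 prints a fixed block of 4 with exactly one placebo, so a volunteer known to be on placebo reveals three block-mates once block boundaries are inferred

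*Combined protocol and SAP*

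**What the plan says.** Section 8.4 gives the ratio ("Volunteers will be randomized using block randomization in a 3:1 ratio of FLSC:placebo"), the block size ("They will be block randomized in groups of 4 with each study group") and the content of each block ("There will be 5 groups of 4 volunteers in each randomized block (each block will have 3 FLSC recipients and 1 placebo recipient"). Read literally, that last sentence puts five groups of four inside one block. Section 4.2 says "Each dose group will have 15 vaccine and 5 placebo recipients", and the only reading that fits is five blocks of 4 per dose group.

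On blinding, Section 8.4.1 says "Both the investigator and the volunteer will be blinded to the study drug/placebo but not to the group assignment". Section 8.4.2 provides two sealed decoding envelopes per volunteer: "One envelope will be retained by the investigator and the other one by the research pharmacy/medical monitor". It allows a code break only for a serious adverse event, and only if knowing the treatment can influence its care. Under Section 11.6 the DSMB can also open envelopes if safety requires it.

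The comparator is described in the Synopsis: "Placebo consisting of preservative free normal saline in volumes equal to the investigational product administered intramuscularly". The vaccine contains aluminum phosphate (Sections 4.1 and 8.1). Syringes are covered, and the injection site is examined at 15 and 30 minutes and again at later visits (Sections 6.1.1.3 and 9.5).

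The Synopsis describes one center. Section 6.3 fills each dose group before the next opens, and Section 6.1.1.3 has volunteers numbered and randomized on site at Visit 1. The documents do not vary the block size, withhold it from blinded staff, or protect block-mates after one assignment becomes known.

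**The concern.** A small fixed block turns information about one volunteer into information about others. With one placebo per block of 4, learning that a volunteer is on placebo settles the other three. The covered syringe does not guard against this, because the inference comes from the block structure.

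What is at stake is mainly unbiased assessment. An investigator grades every adverse event (Section 11.4) and judges its relation to the vaccine (Section 11.3). Severity feeds the primary endpoint, which is the occurrence of severe systemic and severe local reactions (Section 13.4). Relatedness feeds the halting rules in Sections 6.4.1, 6.5 and 7.3.4. With 5 placebo recipients per dose group and 15 in all, a few judgments shaded by a suspected assignment could alter the comparison. Selection bias, through anticipating the next allocation, is possible but weaker, because earlier assignments would have to be recognized before the next volunteer is randomized.

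**Working it through.** **Inputs.** Ratio 3:1, block of 4, 3 FLSC and 1 placebo per block (Section 8.4); 15 and 5 per dose group (Section 4.2); control event rate below 0.1% (Section 13.1). Reaction rates are not given anywhere.

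**The plan's own split.** 20/4 = 5 blocks per dose group; 5 × 3 = 15 FLSC and 5 × 1 = 5 placebo. Over three groups this is 45 + 15 = 60, which agrees with the plan.

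**What one known assignment reveals.** A block has four possible sequences: PFFF, FPFF, FFPF, FFFP.
- One volunteer known to be placebo: one sequence remains, so the other three are FLSC with probability 1.
- One known FLSC: three sequences remain, and each other member's placebo chance goes from 1/4 to 1/3. Nobody is certain.
- Two known FLSC: 1/2. Three known FLSC: the fourth is certainly placebo.

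**Allocations predictable in advance.** If every earlier assignment is recognized, the number certain beforehand is 3, 2, 1 or 1, according to whether placebo comes first, second, third or fourth. The mean is (3 + 2 + 1 + 1)/4 = 1.75 of 4, or 44%. With no recognition it is 0%. The documents do not place the trial within that range.

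**How far a local-reaction clue goes.** Assume, for illustration only, that 50–80% of FLSC and 10–30% of saline recipients react visibly. Then P(placebo | no reaction) = 0.25(1 − s)/[0.25(1 − s) + 0.75(1 − f)], where f and s are the FLSC and saline reaction rates.
- f = 0.5, s = 0.3: 0.175/(0.175 + 0.375) = 32%.
- f = 0.8, s = 0.1: 0.225/(0.225 + 0.150) = 60%.

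A non-reactor is therefore a suspect, not an identified placebo recipient.

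**How often a formal break could expose a placebo recipient.** At the Section 13.1 ceiling of 0.1%, the chance of at least one such event among 15 placebo recipients is 1 − 0.999^15 = 1.5%. Not every such event would justify a break.

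**Alternatives with the same 15/5 split.**
- Block of 8 (6:2): after one known placebo, each of the other seven has a 1/7 = 14% placebo chance, so none is certain.
- Single list of 20: each of the other 19 has 4/19 = 21%. But the chance of no placebo among the first four is C(15,4)/C(20,4) = 1365/4845 = 28%.
- Mixed 4s and 8s: no placebo among the first four can occur only if the first block is an 8, and then with chance C(6,4)/C(8,4) = 15/70 = 21%. In random order this gives 2/3 × 15/70 = 14% for two 8s and one 4, and 1/4 × 15/70 = 5% for one 8 and three 4s. The first eight volunteers always include a placebo.
- Perfect-recognition ceiling for mixed blocks, even if the sizes leaked: a 6:2 block has 6/3 + 2/7 = 2.29 predictable allocations. Two 8s and one 4 give (2 × 2.29 + 1.75)/20 = 32%; one 8 and three 4s give (2.29 + 3 × 1.75)/20 = 38%. Both are below 44%.

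**The case against.** The strongest reply is that certain disclosure will seldom happen. Code breaks are confined to serious adverse events where the answer matters for care, placebo events are expected to be very rare, and breaking an FLSC code makes no one certain. This stands: formal unblinding is the minor route.

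Second, a reader might infer that 44% of allocations are predictable, or that one apparent placebo settles the block. The documents do not support this. Both need reactions to identify treatment perfectly, and 44% also needs each assignment to be recognized before the next randomization. Differences between alum vaccine and saline exist under any block size; the fixed block amplifies a clue but does not create it.

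Third, the documents do not state that numbers are issued in sequence or that one person enrolls, grades and attributes. Replacements (Section 6.1.1.5) could shift block boundaries, and how they are allocated is not described. Boundaries would have to be inferred, although one center and groups filled in turn make that feasible.

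Fourth, much of the safety information is harder to bias. Reactogenicity is also recorded in a volunteer diary (Section 11.1.5.6), and the CD4 rule and laboratory grades rest on numeric measurements. It would also be wrong to say that relatedness drives the primary endpoint, since Section 13.4 defines it by severity alone.

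Finally, small blocks keep concurrent placebo recipients in a first-in-human dose group that may be halted early. That is a sound argument against abandoning blocks. It does not argue for fixing their size or printing it.

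**Conclusion.** The point holds as a cheap improvement to the blinding. It does not show that any estimate, test or sample size is wrong. With boundaries inferred, one known placebo recipient reveals three block-mates exactly, and three known FLSC recipients reveal the fourth; one known FLSC recipient moves the others only from 1/4 to 1/3. The share of allocations predictable in advance is between 0% and 44%, and the documents cannot narrow that range because they give no reaction rates. The conclusion assumes that blinded investigators read Section 8.4 as printed and can count off blocks at the single center, with replacements not obscuring the boundaries. The exposed judgments are severity, for the primary endpoint, and relatedness, for the halting rules; selection bias is secondary.

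**What to change.** Within each dose group, generate the list in randomly ordered blocks of 4 (3:1) and 8 (6:2) that sum to 20, for example two 8s and one 4, or one 8 and three 4s. Keep the sizes and boundaries only in the research pharmacist's randomization file. Replace the block description in Section 8.4 with a statement that randomization is 3:1 in permuted blocks of varying, undisclosed size. This also removes the garbled sentence.

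The ratio, the 15/5 split and the sample size do not change. The work is a new list from the pharmacist and a short text edit. The downside is a slightly less even spread of placebo over enrollment: a 5–14% chance of no placebo among the first four volunteers of a dose group for the two example mixes, against none now. A single unblocked 15:5 list is not recommended, because that chance rises to 28%. Some predictability remains under any list, since the 15/5 totals are printed elsewhere and the last allocations in a group could be deduced if all the others were recognized.
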